15.2. Ethics Committee/Institutional Review Board (EC/IRB) Review

The EC/IRB must be a properly constituted board or committee operating in accordance with 21 CFR Part 56, "Institutional Review Boards." This protocol, any protocol amendments, the associated informed consent forms, and the informed consent procedures must be submitted to the EC/IRB for review and approved before the enrollment of any patient into the trial.

All types of patient recruitment or advertising information must be submitted to Tonix or its designee and to the EC/IRB for review and approval prior to implementation. EC/IRB approval of any protocol amendments must be received before any of the changes outlined in the amendments are put into effect, except when the amendment has been enacted to eliminate a potential hazard to study patients. In such cases, the chair of the EC/IRB should be notified immediately and the amendment forwarded to the EC/IRB for review and approval.

15.3. Written Informed Consent

It is the responsibility of the investigator to obtain signed written informed consent from each potential study patient prior to the conduct of any screening or other study procedures. This written informed consent will be obtained after the methods, objectives, and potential risks of the study have been fully explained to the potential patient. The investigator must explain to each patient that he or she is completely free to refuse to enter the study or to withdraw from it at any time. NOTE: Patients on serotonergic medications (e.g., triptans) should be warned of a potential serious drug interaction and should be advised to contact their study site immediately if they experience any symptoms that might represent possible serotonin syndrome, including fever, confusion or agitation, hallucinations, sweating, high or low blood pressure, rapid heart rate, tremor, muscle rigidity or nausea, vomiting or diarrhea. Patients on MAOIs should not be considered for the study, and MAOIs should not be initiated during the study due to the additional safety concerns posed by this class of medication when used in combination with other serotonergic drugs (such as cyclobenzaprine).

The patient should also be asked in the Informed Consent Form (ICF) for permission for the principal investigator or his designee to contact the patient's other personal physicians, as appropriate, concerning participation in the study.

The method of obtaining and documenting informed consent and the contents of the ICF will comply with International Conference on Harmonization (ICH) Good Clinical Practice (GCP) guidelines, the requirements of 21 CFR Part 50, "Protection of Human Patients," the Health Insurance Portability and Accountability Act (HIPAA) regulations, and all other applicable regulatory requirements. A properly executed written ICF shall be read, signed, and dated by each patient prior to entering the trial or prior to performing any study procedure. The original signed and dated ICF will be kept on file at the study site. Patients will be given a copy of the signed ICF and will be informed of any new developments during the course of the study that might influence their continued participation in the study.

The investigator or a qualified designee will be available to answer each patient's questions throughout the study, and all questions must be answered to the patient's satisfaction. If the protocol is amended and a revised ICF is introduced during the study, each patient's further consent must be obtained. The new version of the ICF must be approved by the EC, prior to subsequently obtaining each patient's consent.

Receipt of written informed consent will be documented in each patient's or potential patient's CRF. The signed ICF must remain in each patient's study file and must be available for verification by study monitors at all times.

Separate written, signed informed consent must be obtained if the patient is to participate in the optional pharmacogenomic assessment.

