Unless otherwise stated, excluded medications (e.g., trazodone, prazosin, topiramate, alpha-adrenergic agonists or antagonists [e.g., prazosin; tamsulosin; terazosin; doxazosin, silodosin, alfuzosin, clonidine, guanfacine], buspirone, benzodiazepines, and non-benzodiazepine hypnotics [zolpidem, zaleplon, eszopiclone]) will require a 1-week drug-free period prior to the Baseline visit (Visit 2). Several benzodiazepines are not easily detected by the in-clinic urine dipstick; therefore, any patient whose screening UDS is positive for benzodiazepines should undergo repeat urine testing after washout, and that sample should be sent to the central laboratory for centralized interpretation. Because of this, the Baseline visit may need to be delayed to provide sufficient time for the results of the repeat, post-washout drug screen to be returned to the site, since the patient should not be randomized until negative results have been confirmed. It is recommended that the Baseline visit is scheduled no sooner than 7 days after the patient's post-washout urine drug screen, to ensure the results are available for review at the Baseline visit.

Similarly, all opioid medications, including tramadol and tapentadol, are excluded medications. Patients on chronic opioids are not appropriate candidates for participation, but there may be patients with occasional PRN opioid usage or who were recently on a short course for acute pain who may be appropriate if, in the clinical judgement of the Investigator, they could be safely tapered and remain opioid free for the week before baseline visit and throughout the 12 weeks of the study. The screening period of up to 21 days is provided to ensure a safe tapering rate and discontinuation of excluded medications, per Investigator's discretion, leading up to the 1-week medication-free period required before the randomization/baseline visit.

Other medications capable of modifying the pharmacologic activity of TNX-102 SL (e.g., α -adrenergic agonists/antagonists; potent CYP3A4 inhibitors) will also be excluded, and discontinuing these medications should only be considered if clinically acceptable. A list of

CYP3A4 inhibitors is provided in [Appendix 2](#); only those considered potent or strong inhibitors (in the left-hand column) are excluded medications.

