8.5.1. Allowed Concomitant Medications

It is ideal to have all patients participating in the study go without any hypnotic agents for the entire double-blind period of the study. Yet there may be instances in which patients' insomnia symptoms need to be addressed with a concomitant treatment. In these instances, the Investigator should recommend use of an antihistamine-based OTC hypnotic, such as Benadryl® or generic diphenhydramine 25-50 mg, for a limited period (e.g. no more than a few nights in a row). Patients should be asked to keep track of their use of such sleeping remedies, and again, chronic nightly use should be avoided whenever possible.

Melatonin is considered an allowable concomitant medication but its usage should have been stable for at least 30 days prior to baseline and usage should remain stable during the study. If diphenhydramine is ineffective, the treating Investigator should contact the medical monitor to discuss alternative options.

Allergy medications and cold remedies containing adrenergic agonist decongestants such as pseudoephedrine or phenylephrine should be avoided unless absolutely necessary (and in such cases when considered absolutely necessary, they should be avoided in the evening or at bedtime to minimize their interference with sleep). Sympathomimetics such as adrenergic agonist decongestants have the potential to acutely worsen PTSD symptoms and therefore could confound the assessment of TNX-102 SL versus placebo for treatment of PTSD.

Other prescription or over-the-counter medications not specifically excluded by entry criteria typically may be continued during the study, with the expectation that chronic medications should have been used in a stable fashion for at least 30 days prior to randomization. Sites should contact the medical monitor for any questions about whether a concomitant medication may be continued during the study or if it would be acceptable to taper an excluded medication.

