APPENDIX 2. LIST OF CYP3A INHIBITORS

Taken from Table 3, FDA Draft Guidance for Industry: Drug Interaction Studies—Study Design, Data Analysis, Implications for Dosing, and Labeling Recommendations; Feb 2012; updated Sept. 26, 2016). Excluded strong CYP3A4 inhibitors are listed in the far left column of the table.

	Strong Inhibitors ≥ 5-fold increase in AUC Or, > 80% decrease in CL	Moderate Inhibitors ≥ 2 but < 5-fold increase in AUC Or 50-80% decrease in CL	Weak Inhibitors ≥ 1.25 but < 2-fold increase in AUC Or, 20-50% decrease in CL
CYP3A4	boceprevir clarithromycin cobicistat conivaptan danoprevir elitegravir grapefruit juice indinavir itraconazole ketoconazole lopinavir mibepradil nefazodone nelfinavir paritaprevir posaconazole ritonavir saquinavir telaprevir telithromycin tipranavir troleandomycin voriconazole	amprenavir aprepitant atazanavir cimetidine ciprofloxacin clotrimazole crizotinib cyclosporine darunavir/ritonavir diltiazem dronedarone erythromycin fluconazole fluvoxamine fosamprenavir imatinib tofisopam verapamil	alprazolam amiodarone amlodipine atorvastatin bicalutamide chlorzoxazone cilostazol fosaprepitant fluoxetine gingko goldenseal isoniazid istradefylline ivacaftor lapatinib lomitapide nilotinib oral contraceptives pazopanib ranitidine ranolazine tacrolimus tipranavir/ritonavir ticagrelor zileuton

Source: Table 3-2,

<https://www.fda.gov/Drugs/DevelopmentApprovalProcess/DevelopmentResources/DrugInteractionsLabeling/ucm093664.htm>

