2 DOSAGE AND ADMINISTRATION

The recommended adult dose for most patients is one (1) AMRIX 15 mg capsule taken once daily. Some patients may require up to 30 mg/day, given as one (1) AMRIX 30 mg capsule taken once daily or as two (2) AMRIX 15 mg capsules taken once daily.

- It is recommended that doses be taken at approximately the same time each day.
- Use of AMRIX for periods longer than two or three weeks is not recommended [see *Indications and Usage* (1)].

Instruct patients to swallow AMRIX capsules intact. Alternatively, the contents of the AMRIX capsule may be sprinkled over applesauce and then swallowed. This method is appropriate only for patients able to reliably swallow the applesauce without chewing.

AMRIX® (cyclobenzaprine hydrochloride extended-release capsules)**5 WARNINGS AND PRECAUTIONS****5.1 Serotonin Syndrome**

The development of a potentially life-threatening serotonin syndrome has been reported with cyclobenzaprine when used in combination with other drugs, such as selective serotonin reuptake inhibitors (SSRIs), serotonin norepinephrine reuptake inhibitors (SNRIs), tricyclic antidepressants (TCAs), tramadol, bupropion, mepерidine, verapamil, or MAO inhibitors. The concomitant use of AMRIX with MAO inhibitors is contraindicated [see *Contraindications* (4)]. Serotonin syndrome symptoms may include mental status changes (e.g., confusion, agitation, hallucinations), autonomic instability (e.g., diaphoresis, tachycardia, labile blood pressure, hyperthermia), neuromuscular abnormalities (e.g., tremor, ataxia, hyperreflexia, clonus, muscle rigidity), and/or gastrointestinal symptoms (e.g., nausea, vomiting, diarrhea). Treatment with AMRIX and any concomitant serotonergic agents should be discontinued immediately if the above reactions occur and supportive symptomatic treatment should be initiated. If concomitant treatment with AMRIX and other serotonergic drugs is clinically warranted, careful observation is advised, particularly during treatment initiation or dose increases.

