
 have heart failure have an overactive thyroid (hyperthyroidism) 
Talk to your healthcare provider before taking this medicine if you have any of the conditions listed above.
	
Before taking AMRIX, tell your healthcare provider about all of your medical conditions, including if you:
 
 have a history of eye problems including glaucoma have heart problems or have had a heart attack have liver problems have trouble emptying your bladder (urinary retention) are pregnant or plan to become pregnant. It is not known if AMRIX will harm your unborn baby. are breastfeeding or plan to breastfeed. It is not known if AMRIX passes into your breast milk. Talk to your healthcare provider about the best way to best way to feed your baby if you take AMRIX. 
Tell your healthcare provider about all the medicines you take including prescription and over-the-counter medicines, vitamins, and herbal supplements.
 
Especially tell your healthcare provider if you take:
 
 a medicine to treat depression, mood, anxiety, psychotic, or thought disorders a pain medicine called tramadol or meperidine barbiturates or other medicines that depress your central nervous system (CNS depressants) a medicine that prevents nerve impulses (anticholinergic medicines) a medicine to help quit smoking called bupropion a blood pressure medicine called verapamil 
Know the medicines you take. Keep a list of your medicines and show it to your healthcare provider or pharmacist when you get a new medicine.
 
How should I take AMRIX?
 
 Take AMRIX exactly as your healthcare provider tells you to take it. Your healthcare provider will tell you how much AMRIX to take and when to take it. Your healthcare provider may change your AMRIX dose if needed. Take AMRIX around the same time every day. Swallow AMRIX capsules whole. If you have difficulty swallowing AMRIX capsules, tell your healthcare provider. Your healthcare provider may recommend opening the AMRIX capsule and mixing the contents with applesauce. AMRIX should only be taken for short periods (up to two or three weeks). If you take too much AMRIX, call your healthcare provider or go to the nearest hospital emergency room right away. 
What should I avoid while taking AMRIX?
 
You should not drink alcohol until you know how AMRIX affects you. Taking AMRIX with alcohol or other medicines that depress your central nervous system can slow your thinking and physical response times.
 
Do not drive, operate machinery, or do other dangerous activities until you know how AMRIX affects you.
 
What are the possible side effects of AMRIX?
 
AMRIX may cause serious side effects, including:
 
 Serotonin syndrome is a serious medical condition that may happen when AMRIX is taken with certain other medicines. Call your healthcare provider right away or go to the nearest hospital emergency room if you have some or all of these symptoms suggestive of serotonin syndrome: 
 agitation, hallucinations, coma, or other changes in mental status coordination problems or muscle twitching (overactive reflexes) fast heartbeat, high or low blood pressure sweating or fever nausea, vomiting, or diarrhea muscle stiffness or tightness 								

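### Section 15.3 does not make clear whether its serotonin-syndrome warning covers verapamil, the one drug on the appended label's list that participants may keep taking

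*Protocol*

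**What the plan says.** Section 15.3 (Written Informed Consent) carries the protocol's own instruction on this interaction: "Patients on serotonergic medications (e.g., triptans) should be warned of a potential serious drug interaction". Those warned are also told which symptoms should make them contact the site at once. MAO inhibitors are dealt with separately: "Patients on MAOIs should not be considered for the study, and MAOIs should not be initiated during the study". The same section requires that, for everyone, the "potential risks of the study have been fully explained to the potential patient" before consent is given.

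On permitted drugs, section 8.5 refers to the CYP3A4 table in Appendix 2 and states that "only those considered potent or strong inhibitors (in the left-hand column) are excluded medications". Verapamil closes the middle column, for moderate inhibitors: "imatinib tofisopam verapamil". Section 8.5.1 gives the default: "Other prescription or over-the-counter medications not specifically excluded by entry criteria typically may be continued during the study".

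Appendix 3 reproduces the label of an extended-release cyclobenzaprine capsule. Its section 5.1 lists the drugs with which serotonin syndrome has been reported, and the list ends "verapamil, or MAO inhibitors. The concomitant use of AMRIX with MAO inhibitors is contraindicated". Sections 7 and 17 repeat the list, and section 17 asks that patients be cautioned about those combinations and told the symptoms. The patient leaflet in the same appendix describes "a blood pressure medicine called verapamil".

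**The concern.** Two parts of one document define the same risk group differently: 15.3 by a pharmacological class with a single example, the label by a list of names. Where a listed drug is excluded from the trial, the difference does no harm. It matters only for a listed drug that participants may take.

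The purpose of 15.3 is prompt self-report. Elsewhere, adverse events are elicited with general, non-leading questions (11.3.1), and after the Week 2 call and the Week 4 visit the scheduled contacts are four weeks apart (Weeks 8 and 12). The label describes the reaction as potentially life-threatening. If the instruction leaves doubt about who is to be warned, a participant could take cyclobenzaprine nightly for 12 weeks with a listed drug and not know that certain symptoms call for immediate contact.

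**Working it through.** The plan gives no figure to reproduce. The check sets each of the eight drugs or classes named in Appendix 3 section 5.1 against the protocol's rules.

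| Named in the label | Protocol rule that applies | May be taken during the study? |
|---|---|---|
| SSRIs | Inclusion 6, exclusion 9 (antidepressants) | No |
| SNRIs | Same | No |
| TCAs | Same; low dose for insomnia needs one week off before Baseline | No |
| Bupropion | Same, taken as an antidepressant | No |
| Tramadol | Exclusion 10; section 8.5 names it | No |
| Meperidine | Exclusion 10, taken as an opioid | No |
| MAO inhibitors | Section 15.3 | No |
| Verapamil | None: absent from exclusions 9 to 11 and from 8.5; moderate column of Appendix 2 | Yes, by default under 8.5.1 |

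Count: 8 named, 7 barred, 8 − 7 = 1 permitted.

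Bupropion and meperidine are placed by drug class, because the entry rules do not name them. If a site did not treat bupropion for smoking cessation as an antidepressant, the number permitted would rise, so this assumption does not create the finding.

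Does 15.3 reach verapamil?

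- Against: it is not named, the only example is triptans, and the leaflet presents verapamil by its use in blood pressure. A site scanning a medication list for serotonergic drugs has no cue to stop at it.
- For: the label's Highlights summarise the section 5.1 list with the class term, and 5.1 itself goes on to speak of other serotonergic drugs after listing verapamil. The example in 15.3 is open-ended. An investigator who had read Appendix 3 closely could include it.

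Both readings are available, so the scope is ambiguous.

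The documents give no rate of verapamil use. Purely as an illustration, assume 0.5% to 2%. With 250 planned participants and at most 120 added after the interim analysis, the total is 250 to 370. Then 0.005 × 250 = 1.25 and 0.02 × 370 = 7.4, or roughly 1 to 7 people, about half of them on active drug under 1:1 allocation. The range comes entirely from the assumed rate.

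**The case against.** The strongest reply is that 15.3 is a general class warning which never set out to copy the label. Its own example, triptans, is not on the label's list. The label belongs to another product, a 15 or 30 mg oral capsule for two to three weeks' use, and the protocol already departs from it on duration and on age. The lay description of verapamil says nothing about class: the same leaflet presents bupropion as an aid to stopping smoking. There are also safeguards. The sponsor's medical monitors review key screening information before authorising randomization (10.1.4), sites may consult them about concomitant drugs (8.5.1), medications are reviewed at every visit (Appendix 1), and a history of serotonin syndrome is excluded (exclusion 18).

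Much of this stands, and it rules out several stronger readings:

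- A reader might infer that patients on verapamil are not warned. The documents do not show that: the consent form is not available for review, and 15.3 requires the risks to be explained to everyone.
- A reader might infer that 15.3 contradicts the label. It does not: the label uses the class term for its own list, so the two can be read as consistent.
- A reader might infer that the protocol must adopt the label's list. Nothing in the protocol says so.
- A reader might bring in CYP3A4 inhibition by verapamil (Appendix 2, and label section 12.3). That is a pharmacokinetic matter and does not bear on who receives this warning.

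What survives is narrower. The protocol chose to append this label, and section 12.4 cites it for the active ingredient. None of the safeguards tells anyone to give the 15.3 warning to a patient on verapamil.

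**Conclusion.** The point holds as an ambiguity in an instruction. Section 15.3 does not name verapamil, the documents allow participants to continue it, and the appended label lists it for this interaction, so a site could comply with 15.3 and not give the warning.

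The size is one of eight listed drugs or classes. The number of people cannot be derived from the documents and is probably small. The conclusion rests on the class placements stated above and on the text available for review; a consent form that already names verapamil would leave only the protocol wording to tidy. Nothing here affects the endpoints, type I error, power or the analysis. It is worth correcting because the labelled reaction is serious and the correction is cheap.

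**What to change.** Reconcile section 15.3, and the matching consent text, with sections 8.5 and 8.5.1 and Appendices 2 and 3. The result should state explicitly how the 15.3 warning applies to any drug on the Appendix 3 section 5.1 list that a participant may be taking; under the present entry criteria that is verapamil. Whether such patients are enrolled, and what they are told, is a clinical decision for the sponsor.

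The cost is about one sentence in the protocol and one in the consent form, with the ethics approval that section 14.1 requires. If the form is revised during the study, section 15.3 also requires each participant's further consent. There is no cost in sample size or analysis.

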16. DATA HANDLING AND RECORDKEEPING

16.1. Maintaining Privacy and Confidentiality

In order to maintain patient privacy, all CRFs, study drug accountability records, and other documents, including communications between the study site and Tonix, will identify patients only by their initials or their assigned study identification numbers. If required, the investigator will grant monitors and auditors from Tonix or its designee and/or regulatory authority's access to patients' original medical records for verification of the data gathered on the CRFs and to audit the data collection process. Patients' confidentiality will be maintained and will not be made publicly available.

Special Provisions for Confidentiality: A Certificate of Confidentiality (CoC) has been obtained from the FDA for the investigators to protect patients enrolled in the study. Investigator can use the Certificate to avoid compelled "involuntary disclosure" (e.g., subpoenas, insurers, employers, or other third parties) of names and other identifying information about any individual who participates as a research patient (i.e., about whom the investigator maintains identifying information) during any time the Certificate is in effect.

